#### **7.2.7 Visit #4 (6-month Study Visit/End of Study Visit)**

The 6-month study visit will be scheduled after MBSR or SME Booster session #4 (end of study). If the 6-month visit cannot be completed in the CRC due to COVID-19, or the preference of the subject, the 6-month visit will be completed remotely using videoconferencing (PSH Teams) and all data that can be collected remotely will be obtained including the home hemoglobin A1c using the Home A1CNow Self Check kit, urine pregnancy test when applicable, diabetes device data, and surveys. At the beginning of the study visit, the blinded research coordinators will remind subjects not to say anything that would

reveal their group assignment e.g. instructors' names, specifics about their classes or Daily Diary survey questions, the PSU Zoom link for their classes, etc.

Subjects will be asked to bring the following to the remote or in-person 6-month visit:

- A list of their current medications and supplements so their current medications and supplements can be recorded
- Their smartphone if they have one
- Their diabetes devices (glucometers, CGM, insulin pump and other smart insulin delivery devices)
- Home A1cNow Self Check kit they were given at their screening or baseline visit
- The optional Actigraph device and wear time log/diary that was mailed to them before this visit so that they could wear the Actigraph for 7 days before the final visit

At the 6-month study visit, subjects will present to the CRC after a 10-hour fast (no food or drink, except for water). Additionally, subjects will be asked not to eat or drink (except for water), chew gum, smoke, brush their teeth, exercise physically, or consume prescription or over-the-counter medications in the 60 minutes prior to the visit (as well as during the last 60 minutes of the visit) to prepare for the collection of saliva samples. Subjects will be asked not to wash their hair for 24 hours before the visit, and not to have their hair cut to a length less than 2 cm, to prepare for the optional collection of 2 cm hair samples. Subjects will be asked not to clip their fingernails for at least 2 to 3 weeks prior to the visit to prepare for the optional clipping of approximately 2 mm of nails from each finger of both hands. Subjects will be asked to remove any nail polish at least 24 hours before the visit.

At the 6-month visit, the procedures in the baseline visit will be repeated as described above in section 7.2.3 entitled "Visit #1 (Baseline Study Visit)" and in **Table 3**. In the CRC, a single blood sample will be obtained and all of the baseline laboratory measurements will be repeated. If a subject forgets to fast, blood will still be drawn and documentation will be made of how many hours it has been since they last had something to eat or drink. Saliva for cortisol and  $\alpha$ -amylase will be collected 1) Just before the study visit starts, and 2) immediately after the study visit ends. Hair and nail samples (optional) will be collected and stored to be analyzed later for cortisol, but they will not be analyzed under this protocol. Physical exam will include measurement of weight, height, waist and hip circumferences, blood pressure, and pulse. Body composition will be measured using a Tanita scale, when possible. The physical exam will only be completed if the study visit is in the CRC.

All subjects will complete self-administered questionnaires as described in the baseline visit. After sitting quietly for 15 minutes they will first complete the Toronto Mindfulness Scale (TMS). Then they will complete the remaining questionnaires: Stress Reduction Expectancy Scale (SRES), Food Craving Questionnaire-Trait-Reduced (FCQ-TR), Walking Enjoyment Scale, Participant Questionnaire, Diabetes Distress Scale (DDS), Perceived Stress Scale-10 (PSS-10), Short Form-12 (SF-12), Positive and Negative Affect (PANAS), GAD-7, PROMIS Sleep Disturbance 8a, Modified Coronavirus Impact Scale, the safety assessment PHQ-9, and Counterfactual Measurement. In addition, questions about Perceived Efficacy, Satisfaction, Engagement and Confidence in the study sessions will be self-administered at the 6-month study visit as described in the 2-month study visit.

The research coordinators will administer the Stress Experience Survey and the Hypoglycemia Survey, collect glucometer, CGM and diabetes device data, and assist subjects in obtaining their home hemoglobin A1c value from the Home A1cNow Self Check kit as described in the baseline visit.

At the end of the 6-month visit, a urine pregnancy test will be administered to female subjects of childbearing potential who do not meet any of the criteria for reasonable certainty of not being pregnant as defined above in the screening visit. Any subjects found to be pregnant will be informed of their pregnancy test results. If the subject has a pregnancy test within 2 weeks before the 6-month visit,

verified in their medical records, the pregnancy test result can be accepted in lieu of repeating the test at the 6-month visit. If the study visit is conducted remotely, and if a pregnancy test result collected within 2 weeks before the study visit is not available, then the subject will be mailed a urine pregnancy test to complete at this visit. Subjects will communicate their urine pregnancy test result to the study team by showing the research coordinator their pregnancy test result as displayed on their urine pregnancy test kit during the ( PSH Teams) live videoconferencing study visit.

Before the 6-month visit, the research coordinators will mail subjects an optional Actigraph device to wear around their waist for 7 days before the visit. Subjects will be asked to return the Actigraph and wear time log/diary at the 6-month visit. If this visit is conducted remotely, subjects will be asked to mail the Actigraph back to the study team, after the 7 day wear time, in a pre-stamped envelope, along with a wear time log/diary. In the 2 weeks before Booster #4, subjects will be emailed by the research coordinator and asked to complete two optional ASA24 dietary recalls (1 weekend and 1 weekday) about their food intake on the previous day.

If a study visit is conducted remotely, or if a subject misses a study visit, the research coordinator will obtain and record any available diabetes device data and outside lab results, including hemoglobin A1c, glucose and Lipid panel.

### **7.3 Duration of Participation**

The duration of an individual subject's participation in the study will be approximately 6 to 8-1/2 months.

## **8.0 Subject Numbers and Statistical Plan**

### **8.1 Number of Subjects**

The number of subjects expected to be enrolled and screened is no more than 520 subjects in order to reach the randomization target of 290 subjects. To assure reaching the study's planned sample size requirement (of 290) we will randomize no more than 320 subjects in total.

### **8.2 Sample size determination**

The primary outcome for this trial is the absolute difference between the two interventions with respect to the mean change in hemoglobin A1c from baseline to month 6 and we consider an absolute difference of 0.5% in this outcome to be clinically meaningful. As this is an individually randomized group treatment trial, correlation among observations within groups (defined here as class cohort), as measured by the intraclass correlation coefficient (ICC), must be taken into consideration (Pals et al., 2008). The variance inflation factor, or design effect, for this type of trial will inflate the sample size by  $1+(1-m)p$ , where  $m$  is the average group size and  $p$  is estimated by the ICC. For both interventions (MSBR and SME), we plan to have the average group size be 18 subjects and expect the ICC=0.08. Thus, the design effect is 2.36. Furthermore, we anticipate that 15% of the subjects will drop-out of the study prior to completion. Incorporating the design effect of 2.36 and the anticipated 15% drop-out, a sample size of 290 subjects (145/intervention) will provide 80% power to detect a clinically meaningful 0.5% absolute difference between the two interventions with respect to the mean change in hemoglobin A1c from baseline to month 6, assuming a standard deviation of 0.9% (Frias et al., 2011) using a two-sided test having a significance level of 0.05.

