**4.2.3 When potential subjects will be recruited.**

We will recruit no more than 520 subjects in order to reach the randomization target of 290 subjects. We expect to reach this target by randomizing 36 subjects by month 30, 72 subjects by month 36, 120 subjects by month 42, 174 subjects by month 48, 230 subjects by month 54, and at least 290 subjects (but no more than 320 subjects) by month 60.

**4.2.4 Describe the eligibility screening process and indicate whether the screening process will occur before or after obtaining informed consent. Screening begins when the investigator obtains information about or from a prospective participant in order to determine their eligibility. In some studies, these procedures may not take place unless HIPAA Authorization is obtained OR a waiver of HIPAA Authorization when applicable for the screening procedures is approved by the IRB. [For FDA regulated studies, consent for any screening activities would need to be obtained prior to screening unless specifically waived by the IRB.]**

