**Retention of Subjects:**

We will use the following strategies to keep subjects engaged throughout the 6 months of the study.

We will offer a new cohort of MBSR and SME control classes approximately every 3 months (4 times a year). We do not anticipate subjects waiting more than 3 months to start a class, except over the summer when wait time may be slightly longer due to vacations and scheduling challenges. We will keep potential study subjects engaged from the start by providing them with the dates and times for the next cohort of classes. Providing the dates and times of the classes early on will keep potential subjects engaged and it will also allow them to plan ahead and begin to make room in their schedule.

Study visits will be scheduled as much as possible in advance, taking into account when subjects will be most available, especially around busy times like holidays, vacations, etc. We will also keep potential subjects engaged by scheduling them for screening in the 10 weeks and 2 days (72 days) before the start of the study intervention (Orientation). Those who meet the eligibility criteria and consent will be kept further engaged by scheduling them for a baseline study visit in the 6 weeks before the start of the study intervention (Orientation).

Subjects will be randomized in the week before the start of the study intervention (Orientation). At that time, the SME instructor will contact the subject by phone to randomize them after answering any questions the subject may have and confirming that the subject is still available to participate in the study.

The SME instructor who randomizes a subject will be the one main point person that the subject can contact with any questions about the study. This will be very important in building rapport with the subject and encouraging retention in the study.

Research staff will contact subjects throughout the study to encourage retention, including:

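### The 80% power matches a subject-level calculation, not the class-level test planned, and the class size of 18 does not fit the accrual schedule; on either reading section 8.2 needs restating, but N need not change

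*Combined protocol and SAP*

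**What the plan says.** Section 8.2 treats the trial as an individually randomized group-treatment design and inflates the sample size for correlation within classes. Its inputs are these:

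- Effect: "we consider an absolute difference of 0.5% in this outcome to be clinically meaningful", where the outcome is the mean change in HbA1c from baseline to month 6.
- Spread and test: "assuming a standard deviation of 0.9" (per cent), "using a two-sided test having a significance level of 0.05".
- Clustering: "we plan to have the average group size be 18 subjects and expect the ICC=0.08", followed by "Thus, the design effect is 2.36". The formula printed for the inflation is 1+(1-m)p.
- Drop-out: 15%.
- Result: "a sample size of 290 subjects (145/intervention) will provide 80% power".

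Section 8.3 fits class cohort as a random effect nested within intervention. Neither section names a degrees-of-freedom method. DSMP section V.C repeats 290 subjects and 80% power with the drop-out allowance, but mentions neither the design effect nor the classes.

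On the pace of the trial, section 4.2.3 schedules "36 subjects by month 30, 72 subjects by month 36, 120 subjects by month 42", then 174 by month 48, 230 by month 54 and at least 290 (at most 320) by month 60. Section 7.2.4, under Retention of Subjects, says "We will offer a new cohort of MBSR and SME control classes approximately every 3 months (4 times a year". The opening of section 7.2.4 gives the same interval.

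**The concern.** A design effect allows for the larger variance that clustering causes. It does not allow for the small number of clusters from which the between-class variance is estimated. When class is a random effect nested within arm, the arm contrast is judged against variation between classes, and its reference distribution has about (classes - 2) df. If the 80% was computed as though there were more than 200 df, it is too high for a trial with about 16 classes.

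The class size matters as well, because it fixes both the design effect and the number of classes. If 18 per class is not what the accrual plan would produce, the design effect of 2.36 and the class count both describe a different trial. The sponsor and the DSMB then cannot tell how much margin the trial has if the ICC exceeds 0.08.

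**Working it through.** **Reproducing the plan's figure.** The inputs are those of section 8.2.

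- Design effect: 1+(m-1)p = 1 + 17 x 0.08 = 2.36. The formula as printed, 1+(1-m)p, gives 1 - 17 x 0.08 = -0.36, so the value is right and the print has a sign slip.
- Two-sample t-test, difference 0.5, SD 0.9, two-sided 0.05, 80% power: 51.8, rounded up to 52 per arm.
- 52 x 2.36 = 122.7; 122.7 / 0.85 = 144.4, rounded up to 145 per arm, 290 in all. This is an exact match.
- The normal approximation, which also ignores the number of classes, gives 51 per arm and 284 or 286 in total, depending on rounding.

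**Power with class-level df at 18 per class.**

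- Completers per arm: 145 x 0.85 = 123.25. Effective n per arm: 123.25 / 2.36 = 52.2.
- Noncentrality: 0.5 / (0.9 x sqrt(2 / 52.2)) = 2.84.
- Subject-level df: 2 x 123.25 - 2, about 244; critical t 1.970; power 80.7%.
- Class-level df: 290 / 18 is about 16 classes, so 14 df; critical t 2.145; power 75.2%.
- If 18 is the size at randomization, the retained size is 18 x 0.85 = 15.3, the design effect is 1 + 14.3 x 0.08 = 2.144 and the effective n is 57.5. Power on 14 df is then 79.1%.

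**Class size implied by the schedule.** Section 4.2.3 gives increments of 36, 36, 48, 54, 56 and 60 per six months. Assume two cohorts per six months (the first 36 subjects included) and one MBSR and one SME class per cohort. Dividing by 4 gives 9, 9, 12, 13.5, 14 and 15 per class. That is 24 classes with a mean of 290 / 24 = 12.1, and no block reaches 18. Classes of 18 need cohorts of 36, hence 290 / 36, or about 8 cohorts; 12 cohorts average 290 / 12, or about 24 subjects.

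**Power by number of cohorts.** Class-level df, ICC 0.08, equal class sizes, 123.25 completers per arm:

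| Cohorts | Classes (df) | Size at randomization | Design effect; power | Design effect with retained size; power |
|---|---|---|---|---|
| 8 | 16 (14) | 18.1 | 2.37; 75.0% | 2.15; 78.9% |
| 9 | 18 (16) | 16.1 | 2.21; 78.7% | 2.02; 82.2% |
| 10 | 20 (18) | 14.5 | 2.08; 81.6% | 1.91; 84.8% |
| 12 | 24 (22) | 12.1 | 1.89; 85.9% | 1.74; 88.4% |

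Weighting the 12-cohort case for unequal class sizes changes 85.9% to 85.2%. Spreading the first 36 subjects over one to four cohorts gives 83% to 89%, and up to 91% with retained class size.

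**Sensitivity to the ICC** (full design effect, class-level df). At ICC 0.10, power is 82% with 24 classes of about 12, against 69% with 16 classes of 18. At ICC 0.12 it is 78% against 64%.

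**The case against.** The strongest reply is that nothing is miscalculated: 290 and 80% follow from the inputs listed, and 2.36 is right for m = 18 and ICC 0.08. That stands. The sign slip is in the printed formula only and did not enter the result.

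Second, the subject-level df is inferred. Section 8.3 also leaves open whether the class effect is an intercept only or may vary over time, so the df of the change contrast is not fixed by the text. This stands as a limit on certainty. However, section 8.2 applies its ICC to the change in HbA1c, and a test that reflects that between-class variation has class-level df.

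Third, 75.2% mixes two bases: 16 classes come from randomized subjects, while the sample is completers and the design effect keeps the randomized size. On one consistent basis the figure is 79.1%, within a point of the claim. That is fair, and it is why a range is given; 75.2% is the result if the printed 2.36 is kept.

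Fourth, a reader might infer that the two points add up and leave the trial underpowered. The documents do not support this. About 16 classes arises only with 18 per class. If the schedule holds, classes are smaller and more numerous, and power exceeds 80% even with class-level df. Nor does the schedule prove 12 per class: no section gives the number of cohorts or of classes per cohort, the interval is approximate, and Retention of Subjects allows somewhat longer waits over the summer.

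**Conclusion.** The point holds as a mismatch between the power statement and the design, not as a failed sample size. At 18 per class, power with class-level df is about 75% with the design effect of 2.36, or about 79% if drop-out also shrinks the classes. If the schedule produces about 24 classes averaging 12, the design effect is about 1.9 and power is about 86-88%; 8 to 10 cohorts give about 75-85%. These are alternatives, and only one can describe the trial.

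The figures rest on the plan's effect, SD, ICC and drop-out, on df equal to the number of classes minus 2, and, for the schedule reading, on one class per arm per cohort and about 12 cohorts. The last two are assumptions.

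It would go too far to conclude that N must rise. At 18 per class with the full 2.36, 80% would need about 322 subjects, just above the cap of 320; with the retained class size, about 296; on the schedule reading 290 is already enough. What is at stake is an accurate power statement and a correct view of the margin against a larger ICC.

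**What to change.** In section 8.2 of the protocol and in DSMP section V.C:

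1. Print the design effect as 1+(m-1)p.
2. State one number and one average size of classes that agree with sections 4.2.3 and 7.2.4, including classes per arm per cohort, and say whether the size is at randomization or among completers.
3. Compute power from a t reference with class-level df, and name that df.
4. Restate the design effect and power to match: about 75-79% if 18 per class is kept, or a design effect of about 1.9 and about 86-88% if the plan is about 24 classes of 12.

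Naming the denominator-df method and the form of the class effect in section 8.3 would keep the test in line with the power statement.

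The cost is protocol wording only, with no change to N = 290. The downside is that the stated power may become slightly less favourable if 18 per class is retained.

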### **8.3 Statistical methods**

Data (i.e., physiologic, behavioral, diabetes-related distress, and mindfulness) will be collected longitudinally in this trial. The time period of primary interest in this trial is the change from baseline to

6-months. Linear mixed effects models, which are subject-specific models, will be fit and contrasts constructed to assess adjusted changes from baseline between interventions over time with respect to these continuous outcomes (e.g., the primary outcome of hemoglobin A1c). The primary contrast of interest is the change in an outcome from baseline to month 6 between the two interventions. However, contrasts will also be constructed to assess the change in an outcome from baseline to other points in time (e.g., month 2) between the two interventions to gauge, for example, if the intervention is effective at month 2. The independent fixed factors for the mixed-effects models will include intervention, time (e.g., baseline, 2 months, 6 months), the randomization stratification factor of insulin vs. non-insulin treated at baseline, and the interaction of intervention with time. The group (class cohort) the participant is assigned will be a nested random effect (i.e., group/class cohort will be nested within intervention) in the mixed-effects models to account for the correlation among observations within groups (class cohorts) inherent in an individually randomized group treatment trial (Pals et al., 2008; Murray et al., 2004). Each class cohort will be characterized by various class sizes, instructors, etc. and thus will be important to account for throughout the duration of the trial wherever possible. The time factor in the models for the vast majority of the outcomes will consist of measurements taken at baseline, 2 months, and 6 months, per subject. An unstructured variance-covariance matrix will be pursued to assess the residual error associated with the repeated measurements over time per participant. If this variance-covariance structure fails to provide model convergence, then others will be explored. Linear mixed-effects models are an extension of ordinary regression models that account for the between- and within-subject correlation inherent in longitudinal trials. Mixed-effects models also appropriately handle the correlation within groups for individually randomized group treatment trials by specifying these groups as random effects. Residual diagnostics will be used to determine the appropriateness of model fit and, if necessary, transformations (e.g., logarithmic) of the outcome will be performed to meet modeling assumptions. If transformations fail to provide adequate model fit then adding splines to the linear mixed-effects models, or using nonlinear mixed-effects models, will be considered.

Following our assessment of the initial fit of the models, we will add covariates to the models to assess their impact, if any, on the intervention outcome effects. Some of the covariates to potentially be considered at baseline include biological sex, age, BMI, race, ethnicity, education, income, Adverse Childhood Experiences (ACEs), trial expectations/reasons for joining the trial, marital status, work status, type of diabetes, number of years with diagnosed diabetes and whether insulin-treated or non-insulin treated. We will also explore potential effects of diabetes-related medication changes that took place during the trial that could have impacted the outcome measure at-hand (and/or self-reported adherence to prescribed diabetes medications). As many diabetes patients take medications to lower their HbA1c, this will be an important factor to control for during analysis.

We will follow the principle of intention-to-treat for all primary analyses. In other words, we will include the data on each randomized participant in the statistical analyses, regardless of whether that participant was fully engaged in the study (e.g. participants who were randomized and withdrew prior to starting their randomized allocation, participants who remained active in the study but were not fully compliant in attending their randomized allocation study sessions, level of home practice engagement, etc.). Secondary analyses may explore subgroups of subjects with higher engagement and/or compliance with their study sessions (e.g. subjects who attended at least 8 out of the first 10 sessions). We may use the observed data to determine if/how participants who completed the study differed from those who did not. Statistical methods to account for differential dropout will be considered, if applicable.

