Randomization to MBSR or SME control will be performed within REDCap using a pseudo-random number generator via the PLAN procedure within SAS software, version 9.4 (SAS Institute Inc., Cary, NC). Personnel in the Department of Public Health Sciences will use the PLAN procedure within SAS software to generate a randomization list using variable-size, random permuted blocks to ensure that the number of subjects in each treatment arm is balanced after each set of B randomized subjects, where B is the block size. Using a 1:1 allocation ratio, there will be 145 subjects assigned to each study group. Randomization will be stratified by insulin vs. non-insulin treated subjects to make sure the two groups are balanced as this is a potential confounder. Personnel in the Department of Public Health Sciences will choose the block sizes without revealing it to any of the blinded investigators or study personnel who will be collecting and reviewing outcomes data. Study group data will be presented in a blinded fashion within DSMB reports.

Randomization to MBSR or SME control will be performed by the SME instructors in REDCap during the Randomization phone call as described below. Study group assignments will not be communicated to research personnel who will be collecting and reviewing outcomes data. The SME instructors will communicate the study group assignments to the subjects and the MBSR instructors. The subjects and instructors will be asked to keep the assignments concealed from the blinded investigators and study personnel. The PI, research coordinators and all study personnel involved in the collection and review of outcomes data will be blinded.

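### In the primary HbA1c model the insulin stratum drops out of the month-6 change contrast and baseline enters only by subtraction, so some precision already collected goes unused

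*Combined protocol and SAP*

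**What the plan says.** Section 8.3 fits linear mixed models, with "contrasts constructed to assess adjusted changes from baseline between interventions over time". The responses are baseline, month 2 and month 6, and the primary contrast is the between-arm difference in change from baseline to month 6. On the fixed part it says: "The independent fixed factors for the mixed-effects models will include intervention, time (e.g., baseline, 2 months, 6 months), the randomization stratification factor of insulin" (versus non-insulin treated), and then adds intervention by time. It states no stratum-by-time term, no constraint on the baseline means and no baseline HbA1c covariate. The residual covariance is unstructured if it converges. On clustering: "The group (class cohort) the participant is assigned will be a nested random effect", with no class-by-visit term stated.

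Further on, the section says "we will include the data on each randomized participant in the statistical analyses", and that after the initial fit "we will add covariates to the models to assess their impact, if any, on the intervention outcome effects". The list of candidates repeats insulin treatment, does not name baseline HbA1c, and does not say in what form covariates will enter.

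Section 7.2.4 says "Randomization will be stratified by insulin vs. non-insulin treated subjects", because insulin treatment is seen as a potential confounder, and places randomization after the baseline measurements. For sample size, Section 8.2 says "we plan to have the average group size be 18 subjects and expect the ICC=0.08" and "assuming a standard deviation of 0.9" per cent, with 15% dropout, an effect of 0.5, 80% power and 145 per arm.

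**The concern.** The stratum was built into the randomization to control for insulin treatment, and the model includes it, so a reader expects the primary contrast to benefit from it. It does not. A main effect that is constant over visits shifts baseline and month 6 equally and vanishes from their difference.

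Baseline HbA1c is also used less well than it could be. With a separate baseline mean per arm, the arm difference at baseline is subtracted in full, although the best coefficient is the regression slope of month 6 on baseline.

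The same mechanism reaches the later covariate step. If baseline covariates enter as main effects only, they will show almost no impact on this contrast by construction, and that could be misread as robustness.

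At stake is precision, not validity.

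**Working it through.** **The plan's own figure.** The design effect is 1 + (18 − 1) × 0.08 = 2.36. (The printed formula has the sign of the class-size term reversed; the value is right.) The normal formula gives 50.9, so 51 per arm, and 51 × 2.36 / 0.85 = 141.6. The t-based count is 52 per arm, and 52 × 2.36 / 0.85 = 144.4, so 145 per arm and 290 in total. The stated figure reproduces.

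**The stratum.** Write the mean for arm a, visit t, stratum s as μ(a,t) + γs. In [μ(M,6) − μ(M,0)] − [μ(S,6) − μ(S,0)] the term γs cancels. Exact generalised least-squares weights (8 classes of 18 per arm, three visits) confirm this. With complete data the weights with and without the stratum differ by about 1e-17. With 15% dropout they differ by at most 0.0001 per observation, and the SE is unchanged to about 0.0001. In simulated trials with 15% dropout the stratum term moved the estimate by 0.001 to 0.002 on average (maximum 0.011).

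**Baseline.** The same weights put −1.00 on the baseline arm difference under the plan. Under a common baseline mean, with class effects after baseline and equal SDs, the weight is −ρ, where ρ is the baseline to month-6 correlation.

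**Size, common baseline mean.** Assumed, because the documents do not give them: ρ from 0.5 to 0.9, and r, the ratio of month-6 SD to baseline SD, from 1.0 to 1.4. The 0.9% is taken as the SD of change.

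- Class variance in the contrast, about 8 classes per arm (145/18): 2 × 0.08 × 0.81 / 8 = 0.0162.
- Participant variance of change: 0.92 × 0.81 = 0.7452 = s0²(1 + r² − 2ρr), with s6 = r·s0 and slope b = ρr.
- With month 6: 145 × 0.85 = 123.25 per arm.
- Separate baseline means: 0.0162 + 2[s6²(1 − ρ²)/123.25 + (1 − b)²s0²/145].
- Common baseline mean: 0.0162 + 2s6²(1 − ρ²)/123.25.
- Power: noncentral t, 14 df, effect 0.5.

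At r = 1.0 and ρ = 0.5, s0² = 0.7452. The terms are 0.0162 + 0.00907 + 0.00257, so the SE is 0.1669. Without the last term it is 0.1590. Power in per cent, separate then common baseline:

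| r | ρ 0.5 | ρ 0.7 | ρ 0.8 | ρ 0.9 |
|---|---|---|---|---|
| 1.0 | 79.6, 83.2 | 79.3, 81.5 | 79.2, 80.6 | 79.1, 79.8 |
| 1.2 | 79.3, 81.1 | 79.0, 79.5 | 78.9, 79.0 | 79.0, 79.3 |
| 1.4 | 79.1, 79.9 | 78.9, 78.9 | 79.0, 79.3 | 79.3, 81.6 |

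Before rounding, the gain runs from 0.0 to 3.7 points and is never negative. It vanishes where the slope b is close to 1, since subtraction is then already optimal. At ρ 0.5 to 0.7, a three-visit calculation with none, half or all of the dropouts giving a month-2 value left the gains checked unchanged to 0.1 point. The largest SE reduction is 4.7% here, and 5.0% with complete data.

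**Size, insulin by visit.** With 60% on insulin (assumed), the term removes 0.6 × 0.4 × gap² / 0.7452 of the participant variance. That is 0.3%, 2.9% and 8.1% for gaps in mean change of 0.1, 0.3 and 0.5 (assumed). Power rises by about 0.05, 0.5 and 1.3 to 1.4 points, and by nothing at gap 0. If the term is useless, it raises the SE by about 0.0001 on 0.163.

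**The class term.** A class intercept constant over visits also cancels from the change contrast. With 144 per arm and complete data, the model SE is then √(2 × 0.7452/144) = 0.102. If class variance in fact arises after baseline, the true SE is √(0.01035 + 0.0162) = 0.163. A common baseline mean does not cure this: 0.097 to 0.099 reported against 0.158 to 0.160 true.

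**Later covariates.** For a binary covariate with 30% prevalence and a gap in mean change of 0.5 to 0.8 (both assumed) and 15% dropout, a main effect moved the contrast by 0.001 on average (maximum 0.007). The covariate by visit moved it by 0.026 to 0.034.

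**The case against.** A reader might infer that the contrast is unadjusted for baseline HbA1c. It is not: it subtracts baseline in full. At the participant level, with equal SDs and complete data, the variance in units of σ² (no adjustment, change score, common baseline) is 1, 0.60, 0.51 at ρ = 0.7 and 1, 0.40, 0.36 at ρ = 0.8. The plan therefore already secures 0.40/0.49 = 82% to 0.60/0.64 = 94% of the available reduction. Only at ρ = 0.5 does it secure none. A reader might also take 'adjusted' as a misdescription, but Section 8.3 does not define the word, and it can simply mean model-based.

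The power figures rest on placing the class variance of Section 8.2 in the change contrast, which Section 8.3 does not state. That objection stands. If the class effect is a constant intercept, nominal power is about 99% under either model and says nothing useful. What remains is an SE of 0.107 against 0.102 with 15% dropout, a 4% reduction in the best case (r = 1.0, ρ = 0.5).

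The gain also depends on quantities the documents do not give and may be nil; that stands too. The covariate point is conditional, since the plan does not rule out by-visit terms.

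**Conclusion.** The point holds as one of efficiency, to be considered rather than required. The insulin main effect does nothing for the primary contrast: exactly so with complete data, negligibly otherwise with 15% dropout. Baseline HbA1c enters by subtraction, not regression.

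Under the stated assumptions the unused precision is worth 0 to 3.7 points of power, or 0 to about 5% in SE, from a common baseline mean, and 0 to 1.4 points from insulin by visit. The lower ends are real possibilities.

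The documents do not support a reading of bias or of a wrong sample size. Randomization protects the contrast, leaving out the stratum-by-visit term leans conservative, and 290 reproduces without any of this gain. How the class effect enters over visits matters more for the reported SE than either change does.

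**What to change.** In Section 8.3, for the primary analysis:

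- Use a common baseline mean across arms (a constrained longitudinal model), or model months 2 and 6 with baseline HbA1c by visit as a covariate. Either is valid because baseline is measured before randomization (Section 7.2.4).
- Enter the insulin stratum by visit.
- Keep the month-6 between-arm difference as the primary contrast. It estimates the same effect under Section 1.2 (HbA1c at 6 months) and Section 8.2 (difference in mean change).
- State that the class effect acts on the post-baseline visits. The other changes do not settle this.
- If baseline covariates are added later to assess their impact on the intervention effect, enter them by visit.

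The cost is SAP wording and up to two extra fixed-effect parameters for insulin by visit, with negligible cost in SE. A common baseline mean removes a parameter. Baseline HbA1c, the stratum and the listed covariates are already collected.
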